6.4.5 Laboratory safety assessment

Blood and urine samples for determination of clinical chemistry, haematology and urine analysis, will be taken at the times indicated in the Study Plan, see [Table 1](#).

6.4.5.1 Regular laboratory safety monitoring

A full laboratory screen with blood and urine samples for determination of clinical chemistry, haematology and urine analysis parameters will be taken at visit 1 (including *H. pylori* serology), visit 2, visit 4, visit 6 and visit 7. If an early discontinuation visit is done, a full laboratory screen (including a urine pregnancy test for women of childbearing potential) should be performed.

If there is an unscheduled visit and depending on the reason for this visit, it is the judgement of the investigator to decide if laboratory samples need to be taken to ensure safety monitoring. A limited laboratory screen will be taken at visit 3 and visit 5 to include the following analysis: AST, ALT, ALP, total BIL and CK. Patients with elevated liver transaminases > 3 x ULN will be closely monitored, see Section [6.4.5.2](#).

A urine pregnancy test for women of childbearing potential will be conducted at visit 1, 2, 7 and at early discontinuation visits.

The laboratory samples will be analysed at a central laboratory (Quintiles), except for the urine tests. These tests will be done by dipstick at the study site and the results will be entered into the appropriate modules in the eCRF. See Section 7.1 for the total volume of blood that will be drawn from the patients throughout the conduct of the study.

Table 2 Laboratory safety variables, full laboratory screen

Clinical chemistry	Haematology
S-Aspartate aminotransferase (AST)	B-Haemoglobin (Hb)
S-Alanine aminotransferase (ALT)	B-Red blood cell (RBC) count
S-Alkaline phosphatase (ALP)	B-Erythrocyte mean cell volume (MCV)
S-Total bilirubin (BIL)	B-Mean corpuscular haemoglobin concentration (MCHC)
S-Creatinine	B-White blood cell (WBC) count
S-Blood urea nitrogen (BUN)/urea	B-neutrophils count
S-Albumin	B-eosinophils count
S-Sodium	B-basophils count
S-Potassium	B-lymphocyte count
S-Magnesium	B-monocyte count
S-Calcium	B-Platelet count
S-Creatinine kinase (CK)	
S-C-reactive protein (CRP)	Urinalysis (dipstick)
S-Non-fasting serum glucose	U-Protein
H. pylori antibody immunoglobulin G (IgG) test ^a	U-Glucose
	U-Haemoglobin
	Urine pregnancy test ^b (dipstick)

^a Conducted at visit 1 only.

^b Conducted at visit 1, visit 2, visit 7 and early discontinuation visits only for women of childbearing potential.

Laboratory values outside the reference ranges suspected to be of any clinical significance could be re-checked during an unscheduled visit. Randomized patients who develop clinically significant abnormal laboratory values must be followed until normalization or for as long as the investigator considers necessary.

6.4.5.2 Handling of patients with elevated liver transaminases

The investigator will be alerted from the central laboratory regarding patients developing ALT or AST > 3 x ULN during the study ie, all values above > 3 x ULN with no upper limit will be alerted. How to handle these patients is described in detail in this section.

All patients, regardless of whether they stop or continue the intake of IP, must be closely monitored with repeated laboratory liver tests every third day or more frequently if judged necessary by the investigator until the liver tests begin to improve. Thereafter liver tests will be performed at an interval decided to be appropriate by the investigator. All patients must be followed until the liver tests have returned to baseline or until a firm explanation (diagnosis) to the elevated liver transaminases has been established.

The specific laboratory kit, (Liver kit 1) to be used for confirmation and monitoring includes ALT, AST, ALP, BIL, conjugated BIL, INR, albumin, CK, Hb, WBC, neutrophils, eosinophils, basophils, lymphocytes, monocytes, sodium, potassium and creatinine.

- **Patients who can continue the intake of IP**

- Patients with ALT or AST $> 3 \times$ ULN but $\leq 5 \times$ ULN and no clinical signs or symptoms indicating liver dysfunction can, at the discretion of the investigator, continue the intake of IP with close monitoring.

The patients must be brought back to the clinic for an unscheduled visit without any delay, but not later than 72 hrs after the test results have been received, for specific evaluation of the underlying cause for the ALT or AST elevation and confirmatory laboratory testing.

A medical history focused on risk factors for liver injury (alcohol consumption, exposure to toxic agents, infections, medications and drug use including herbal remedies etc) should be obtained, evaluation of recent symptoms (AEs) and physical examination should be done and all relevant information should be captured in appropriate eCRF modules.

Confirmatory laboratory testing should be done and more frequent monitoring of liver tests should be initiated.

- **Patients who stop intake of IP**

Patients with the following findings should immediately be contacted and instructed to stop intake of IP:

- ALT or AST $> 5 \times$ ULN
- ALT or AST $> 3 \times$ ULN in combination with BIL $> 2 \times$ ULN
- ALT or AST $> 3 \times$ ULN with clinical signs or symptoms indicating liver dysfunction (such as nausea, fatigue, right upper quadrant pain or tenderness, fever, rash or eosinophilia).

The patients must be brought back to the clinic for an unscheduled visit without any delay, but not later than 72 hrs after the test results have been received, for specific evaluation of the underlying cause of the ALT or AST elevation and confirmatory laboratory testing.

A medical history focused on risk factors for liver injury (alcohol consumption, exposure to toxic agents, infections, medications and drug use including herbal remedies etc) should be obtained, evaluation of recent symptoms (AEs) and physical examination should be done and all relevant information should be captured in appropriate eCRF modules.

Confirmatory laboratory testing should be done and more frequent monitoring of liver tests should be initiated.

In addition, the following blood samples (Liver kit 2) for differential diagnosis purposes must be taken in all patients who stop intake of IP:

- Alcohol misuse: carbohydrate deficient transferrin (CDT), S-ethanol
- Viral hepatitis: anti-HAV-IgM, HBsAg, anti-HBc-IgM, anti-HCV, HCV RNA, EBV VCA IgM + EBNA IgG, anti-CMV-IgM
- Autoimmune hepatitis: ANA, AMA, SMA, IgG, IgM, IgA
- Hereditary disorders: S-Iron and TIBC, S-Ferritin, ceruloplasmin, alfa1-antitrypsin.

Imaging techniques and additional examinations can be done if there is a clinical indication as judged by the investigator (eg, ultrasound, CT, liver biopsy). The results of all testing should be entered in the appropriate eCRF modules. It is important that every effort is made to find an explanation for the elevated liver enzymes.

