A physical examination including weight will be performed. A dECG recording followed by an orthostatic test, full laboratory screen, PK sampling and AE recording followed by active questioning (see Section 6.4.3.2) will be done.

After intake of IP, additional PK samples will be taken at 2 hours (± 30 min) and 4 hours (± 30 min) post-dose, see Section 6.6.1. An orthostatic test will be repeated 2 hours (± 15 min) post-dose (at expected t_{max}). N.B. no dECG will be recorded prior to the orthostatic test post-dose at visit 6.

Drug accountability will be performed after the last morning dose has been administered. A follow-up endoscopy will be performed within 5 days for those patients who had evidence of mucosal breaks at baseline endoscopy.

Visit 7 (End of study visit)

Two weeks (± 2 days) after visit 6, a visit 7 will be scheduled for physical examination, a dECG recording followed by an orthostatic test and a full laboratory screen. Women of childbearing potential will undergo a urine pregnancy test. Any ongoing AEs will be followed up by the investigator as long as medically indicated.

Important safety information regarding visit 2-7

- Following the spontaneous AE collection, there will be active questioning to determine whether patients experienced any episode of the following: syncope,

felt faint, lightheadedness or dizziness, see Section 6.4.3.2. The active questioning at visit 2 will be asked prior to first dose of IP.

- For instructions of handling of symptoms occurring during orthostatic tests, see Section 6.4.3.4.
- For handling of patients who spontaneously report symptoms of paraesthesia, see Section 6.4.3.1.
- Patients who have ALT or AST > 3 x ULN must be closely monitored and followed-up until they return to baseline according to a pre-specified handling plan, see Section 6.4.5.2.

Information on population PK sampling at visit 4 and 6

PK samples will be taken at visit 4 (after 2 weeks treatment) and at visit 6 (after 4 weeks treatment); pre-dose in the morning and then two additional samples, at 2 hours (± 30 min) and at 4 hours (± 30 min) post-dose, see Section 6.6.1.

It is very important, for the population PK analysis that:

- the patients are instructed to record the exact time of dose intake in the evening before the study visit and this information will be entered in the eCRF
- the exact time of dose intake in the morning is recorded and transferred to the eCRF by the site personnel

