Since there is always a risk involved in testing new compounds in patients, safety precautions are taken by applying strict exclusion criteria and pre-specified discontinuation criteria. An internal safety committee will perform medical surveillance of AEs, ECG, orthostatic test and laboratory variables on blinded treatment data continuously throughout the study. In addition, an independent Data Safety Monitoring Board (DSMB) will review treatment data during the course of the study (see Section [12.4](#)).

Evaluation for hemodynamic effects will be done through frequent monitoring of dECGs and orthostatic tests. To further appreciate and understand the incidence of symptoms that may be associated with hemodynamic effects, active questioning will be solicited from all patients, see Section [6.4.3.1](#). Any patient experiencing a severe hemodynamic episode will be subject to discontinuation of the IP, see Section [5.8](#). Strict exclusion criteria for heart disease and ECG abnormalities will be applied. Patients with QTcF > 450 ms should not be randomized and patients with QTcF \geq 500 ms during treatment should discontinue intake of IP.

Liver tests will be obtained weekly during the treatment period in this study with criteria for more frequent laboratory monitoring and for discontinuation of the IP applied in the event of significantly increased liver enzymes in any patient, see Section [6.4.5.2](#).

General medical history information will be collected prior to enrolment in the study, with specific questions to identify previous episodes of paraesthesia. Patients with current neurological disorders will be excluded. All patients reporting paraesthesia during the study will be subjected to additional questioning about their symptoms and will undergo an extra physical examination by the investigator. Patients experiencing episodes of paraesthesia for 7 consecutive days will discontinue the IP and be referred to a board certified neurologist, see Section [6.4.3.1](#).

In order to describe endoscopic findings in this target population, a baseline endoscopy will be performed in all patients unless the patient has had an endoscopy within 2 years without mucosal breaks in the most recent examination. In the other patients, only historical endoscopy report data will be collected. In addition, those patients with mucosal breaks at the

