5.8 Discontinuation of investigational product

Patients may be discontinued from IP in the following situations:

- Patient decision. The patient is at any time free to discontinue treatment, without prejudice to further treatment
- AE
- Severe non-compliance to study protocol
- Incorrectly randomized patient, see Section 5.3
- Development of any of the following study specific criteria for individual patients, which **must** lead to discontinuation of IP:
 - Patient experiencing symptoms of paraesthesia daily for at least 7 consecutive days, see Section 6.4.3.1
 - Patient experiencing a syncopal episode (loss of consciousness) from any cause
 - Patient describing an AE of pre-syncope or dizziness as severe. Orthostatic dizziness provoked during testing would not automatically discontinue a patient unless this continued without provocation from orthostatic testing (eg at home when getting up)
 - Patient with a corrected QT interval (QTcF) ≥ 500 ms
 - Patient with ALT or AST $> 5 \times$ ULN, see Section 6.4.5.2

- Patient with ALT or AST >3 x ULN in combination with BIL >2 x ULN, see Section 6.4.5.2
- Patient with ALT or AST >3 x ULN and clinical signs or symptoms indicating liver dysfunction, see Section 6.4.5.2
- AstraZeneca may decide to stop a dose group in the study based on a recommendation from the DSMB. The following criteria, included in the DSMB charter, serve as a guide for the DSMB to stop a dose group. However, a more restrictive approach may be applied based on the DSMB's and AstraZeneca's evaluation during the study:
 - two or more unique events of syncope in different patients in the same dose group that cannot definitively be attributed to another cause (eg, syncope while having blood drawn would be attributable to the blood draw, not the investigational product)
 - corrected QT interval (QTcF) \geq 500 ms in 20% of the planned total number of patients to be enrolled in the same dose group.
 - dizziness causing discontinuation from the IP in 10% of the planned total number of patients to be enrolled in the same dose group.

If a dose group is stopped, any treatment group(s) on a higher dose will also be stopped.

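### The rule allowing study drug to continue after a transaminase rise (Protocol 6.4.5.2) omits the bilirubin limit that the stop rules impose

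*Protocol*

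**What the plan says.** Protocol 6.4.5.2 (Handling of patients with elevated liver transaminases) starts from a central laboratory alert, triggered by ALT or AST above 3 x ULN, and then gives two branches.

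- **May continue.** ALT or AST above 3 and up to 5 x ULN. Such patients with "no clinical signs or symptoms indicating liver dysfunction can, at the discretion of the investigator, continue the intake of IP with close monitoring".
- **Stop.** Patients with any of three findings "should immediately be contacted and instructed to stop intake of IP". The findings are (i) ALT or AST above 5 x ULN, (ii) ALT or AST above 3 x ULN with bilirubin above 2 x ULN, and (iii) ALT or AST above 3 x ULN with clinical signs or symptoms of liver dysfunction, "such as nausea, fatigue, right upper quadrant pain or tenderness, fever, rash or eosinophilia".

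Protocol 5.8 (Discontinuation of investigational product) repeats the three findings at the same thresholds. They fall under "Development of any of the following study specific criteria for individual patients", a list that must lead to discontinuation. The bilirubin item there reads "Patient with ALT or AST >3 x ULN in combination with BIL >2 x ULN", with no symptom condition.

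Other sections send the reader to 6.4.5.2. Section 3.2 does so for criteria "for discontinuation of the IP applied in the event of significantly increased liver enzymes in any patient". Section 3.1 says that patients above 3 x ULN are to be "followed-up until they return to baseline according to a pre-specified handling plan". Each liver item in 5.8 also cross-refers to 6.4.5.2.

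**The concern.** The first branch is evidently meant to hold the patients who meet none of the three stop findings. It carries over the 5 x ULN ceiling and the absence of symptoms, but not the bilirubin limit. It thus offers the investigator a discretion that the stop list and 5.8 take away.

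The combination left open, raised transaminase with raised bilirubin, is one that the protocol itself singles out for stopping. The laboratory alert is defined by ALT or AST alone, so the site has to apply the bilirubin limit itself, and the first branch it reads does not mention one. If a site acted on that branch, two things would follow: dosing would go on against a mandatory stop, and the second set of liver samples (Liver kit 2) could be missed, since those samples "for differential diagnosis purposes must be taken in all patients who stop intake of IP".

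The compound's own data give some reason for care. Section 1.4 reports mild, reversible ALT and AST increases in some healthy subjects at 400 and 800 mg bid for 5 days, which is above the doses studied here.

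**Working it through.** No figure in the plan needs reproducing. The check is one of logic.

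**Inputs.** The may-continue and stop conditions come from 6.4.5.2, and the mandatory list from 5.8. Let P be the higher of ALT and AST, in multiples of ULN, so that the 5 x ULN ceiling caps the transaminase elevation as a whole. Let B be bilirubin in multiples of ULN, and S be clinical signs or symptoms (yes or no).

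- Continue, as written: 3 < P ≤ 5 and S = no.
- Stop: P > 5; or P > 3 and B > 2; or P > 3 and S = yes.

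**Each stop finding against the continue conditions.**

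| Stop finding | Condition that would exclude it from the continue branch | Present? |
|---|---|---|
| P > 5 | P ≤ 5 | Yes |
| P > 3 and S = yes | S = no | Yes |
| P > 3 and B > 2 | B ≤ 2 | No |

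**All combinations with P > 3.**

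| P | B | S | Continue as written | Stop |
|---|---|---|---|---|
| >3 to 5 | ≤2 | no | yes | no |
| >3 to 5 | >2 | no | **yes** | **yes** |
| >3 to 5 | ≤2 | yes | no | yes |
| >3 to 5 | >2 | yes | no | yes |
| >5 | either | either | no | yes |

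The overlap is the second row and no other. Worked example: ALT 4, AST 1, bilirubin 2.5, no symptoms. Since 3 < 4 ≤ 5 and S = no, the continue branch applies. Since 4 > 3 and 2.5 > 2, the stop finding applies too.

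**After adding B ≤ 2 to the continue branch.** The second row becomes stop only. No combination with P > 3 falls under both branches, and none falls under neither.

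**Is the bilirubin value available when the rule is applied?** Yes. Section 6.4.5.1 puts total bilirubin in the limited screen at visits 3 and 5, and Table 2 puts it in the full screen at the other scheduled laboratory visits.

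**The case against.** The strongest reply is that nobody following the whole section would go wrong. The continue branch only permits, whereas the stop list directs and 5.8 compels. An investigator who stops the patient complies with all three texts. The two branches sit next to each other, and the thresholds agree between 6.4.5.2 and 5.8. This stands: the stop rule governs, and a reader who inferred two irreconcilable instructions, or a missing stop criterion, would be going beyond the text.

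Much of the safety handling is also the same in both branches. The clinic visit within 72 hours, the confirmatory tests, and liver tests every third day until improvement begins apply to everyone, and Liver kit 1 includes bilirubin. Under 12.4 a joint safety committee reviews blinded laboratory data every second week. This stands too, and it limits the harm.

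It might also be said that raised bilirubin is itself a clinical sign, since the examples of signs are open-ended and include a laboratory finding, eosinophilia. This does not stand. Both 5.8 and 6.4.5.2 list bilirubin as a criterion separate from signs and symptoms.

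A reader might infer a second gap: because the branch says ALT or AST, a patient with ALT 4 x and AST 6 x ULN could be thought to qualify through ALT alone. The text does not support this on any natural reading. The 5 x ULN ceiling is a cap on the transaminase elevation, and the first stop item a few lines later removes anyone with either enzyme above 5 x ULN.

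**Conclusion.** The point holds in a limited form. As worded, the may-continue branch of 6.4.5.2 gives discretion to keep a symptom-free patient on drug with a transaminase above 3 and up to 5 x ULN and bilirubin above 2 x ULN, although the same section and 5.8 require that patient to stop. It is an incomplete exception to rules that are otherwise complete and consistent.

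The expected size is small. Section 4.2 excludes patients with AST or ALT above 2 x ULN, or bilirubin above 1.5 x ULN, at visit 1, and treatment lasts 4 weeks, so few should reach the combination. The protocol gives no rate from which a number could be worked out. Sample size, significance level, power and the efficacy analysis are not affected.

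The conclusion assumes that the 5 x ULN ceiling applies to the higher enzyme, and that raised bilirubin is not counted among clinical signs. It is a minor correction, but to a stated safety rule that gives the wrong action if its first branch is applied alone.

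**What to change.** In the may-continue bullet of 6.4.5.2, add the condition *and BIL ≤2 x ULN*. Alternatively, add *and not meeting any of the stop criteria below*, which would also settle any doubt about how the two enzymes are read together. Leave the stop criteria in 6.4.5.2 and 5.8 unchanged.

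The cost is one bullet reworded. No threshold, visit, laboratory kit or analysis changes.

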6.4.6 Physical examination

A complete physical examination will be performed at visit 1, 6, 7 and at early discontinuation visits and include an assessment of the following: general appearance, skin, head and neck including throat, lymph nodes and thyroid, abdomen, musculoskeletal/extremities, lungs, cardiovascular, respiratory and neurological systems including cranial nerves.

A complete physical examination as described above must be done in all patients reporting symptoms of paraesthesia, see Section 6.4.3.1.

6.4.7 ECG

The dECGs will be recorded at all visits including early discontinuation visits before orthostatic test and blood sampling. At visit 2, when the dECG will be performed both pre-dose and at estimated t_{\max} (2 hours \pm 15 min post-dose), the ECG electrodes should remain on the patient to ensure that the same position is used for both dECG recordings. After the patient has been supine for at least 10 min, three standard 12-lead dECG recordings (triplicate) will be performed within a 5-minute period while the patient remains supine.

The central vendor (ERT) will provide the equipment (ELI-150) for recording and evaluation of dECGs. The ECG equipment will allow for both digital transfer of the data for central evaluation and for paper print-outs (paper speed 25mm/sec) for the investigator's judgement.

The investigators judgement will be used for enrolment /randomization by classifying the ECG as "normal" or "abnormal", whether any abnormality is clinically significant or not.

All dECGs will be electronically submitted by the investigator to ERT. Once received at ERT the patient's demography and visit information on the ECGs will be checked for inconsistencies and possible errors. Queries will be sent to the sites if necessary to clarify the data before the ECG can be analyzed. If no queries are needed, or once all queries on the ECG are resolved, ECG's will be analyzed using the 3 beats on lead II methodology, performed by a cardiac safety specialist who will select beats and place calipers to produce the interval duration measurements. The ECG then passes to a cardiologist for review. The cardiologist will check for correct beat selection and caliper placements, and also reviews the morphology and note any findings. The turn around time for the complete analysis is 72 hours starting from when the ECG is received at ERT. This time is paused however whilst there are any outstanding queries, and will start again once these are resolved.

ECG reports will be provided to the sites (preferably by e-mail although fax is possible) once the analysis is complete. The reports will contain the mean interval duration measurements, the ERT cardiologist's findings, as well as an evaluation of the ECG (normal, abnormal, unable to evaluate). The standard interval duration measurements produced from a good quality ECG are PR, RR, QRS, and QT. The report will also contain the derived HR, QTcB and QTcF values. It is the investigator's judgement whether the findings/results on the ERT report are clinically relevant or not and whether the findings will result in the discontinuation of the patient from the study based on the inclusion/exclusion or discontinuation criteria.

